### **5.1. MTX Population**

The MTX population will include all subjects who take at least one dose of MTX.

The MTX population will be used for analysis of safety data during the Tolerability Assessment Period prior to randomization and the concentrations of MTX polyglutamate.

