#### 9.4.9. Change from Baseline in sUA

Observed values and change from baseline at each scheduled time point, including pre-infusion and post-infusion results for sUA will be summarized using descriptive statistics (i.e. n, mean, standard deviation, median, 25th quartile, 75th quartile, minimum, and maximum). Changes from baseline for pre-infusion sUA (or available sUA at visits with no infusion, e.g., Weeks 21 and 23) to each visit and overall will be analyzed with an MMRM ANCOVA model as described in [Section 9.4](#).

Line plots of the observed mean pre-infusion sUA values with 95% CI at each scheduled visit will be presented using the ITT population by pegloticase treatment status (On Treatment and Overall) and treatment group. A graphical presentation of the mean pre-infusion sUA values by treatment group and Month 6 sUA responders vs. non-responders, based on the primary endpoint definition of Month 6 response, will also be produced for the ITT population.

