### **10.2. Pegloticase and MTX PK**

For all subjects, serum samples for PK analysis of pegloticase will be collected after the end of infusion on Day 1 (prior to discharge); prior to the pegloticase infusion and after the end of infusion (prior to discharge) at the Weeks 2, 6, 14, 21, 24, 36, End of Pegloticase Infusions Visit (if applicable) and Week 52/End of Study/Early Termination Visits. NOTE: Week 21 Visit and the End of Pegloticase Infusions Visit (if applicable) and Week 52/End of Study/Early Termination Visits are non-infusion visits.

Blood samples for MTX polyglutamate analysis will be collected prior to the pegloticase infusion on Day 1 and at the Weeks 14, 24 and 36 Visits during the Pegloticase + IMM Period .

The following presentations of subject pegloticase and MTX polyglutamate concentration data covered in this SAP will be provided:

This document is confidential.

- A listing including subject, week/time point (actual, planned), treatment and serum concentrations. End of infusion sampling times are expressed relative to the start time of infusion.
- A table summary of pegloticase and MTX polyglutamate concentrations at each time point (n; mean, SD, coefficient of variation (CV)% calculated as  $100\% \times SD/mean$ , minimum, 25th percentile, median, 75th percentile and maximum) for the PK Population or MTX Population, respectively.

Concentrations below the limit of quantification (BLQ) collected on Day 1 pre-dose will be summarized as zero. For the summary of pegloticase concentrations, all other concentrations BLQ will be imputed as half of the lower limit of quantification value. For the summary of MTX polyglutamate concentrations, all post-baseline concentrations BLQ will be excluded from analysis. The number of BLQ values will be presented for pegloticase and MTX summaries.

Concentrations for pegloticase will be summarized by treatment group for the PK Population. Further, the mean and CV% of pegloticase concentrations will be provided by visit and by treatment group in the subset of subjects who are ADA positive (defined as positive for anti-PEG or anti-uricase antibodies at any visit during the study) and ADA negative (defined as negative for both anti-PEG and anti-uricase antibodies for all visits during the study) for each visit.

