Concentrations of MTX polyglutamate are measured for 5 active metabolites (MTX-PG1, MTX-PG2, MTX-PG3, MTX-PG4, MTX-PG5). Concentrations will be summarized for each of the individual metabolites, the sum of MTX-PG1 and MTX-PG2, the sum of MTX-PG3, MTX-PG4, and MTX-PG5, the sum of MTX-PG4 and MTX-PG5, and the sum over all 5 metabolites will be summarized for the MTX Population overall and by Month 6 sUA responders and non-responders. The mean PG3 and PG3-5 concentrations over time, by Month 6 sUA responder subgroup will be plotted.

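### SAP 10.2 compares methotrexate polyglutamate levels between Month 6 responders and non-responders with no stated arm split, so the Day 1 contrast can partly reflect randomized arm (minor)

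*SAP*

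**What the plan says.** SAP 10.2 has MTX polyglutamates measured before the pegloticase infusion on Day 1 and at Weeks 14, 24 and 36. The individual metabolites and several sums "will be summarized for the MTX Population overall and by Month 6 sUA responders and non-responders". It adds: "The mean PG3 and PG3-5 concentrations over time, by Month 6 sUA responder subgroup will be plotted". The population is defined in SAP 5.1: "The MTX population will include all subjects who take at least one dose of MTX". SAP 3.5 and 3.8 give open-label MTX to all subjects from Week -6 to Week -4, so every placebo-arm subject who took a dose belongs to it.

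Elsewhere the authors name the arm. For pegloticase, SAP 10.2 says: "Concentrations for pegloticase will be summarized by treatment group for the PK Population". For uric acid, SAP 9.4.9 plots "mean pre-infusion sUA values by treatment group and Month 6 sUA responders vs. non-responders".

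Three handling rules in SAP 10.2 matter, where BLQ means below the limit of quantification:
- Day 1: "Concentrations below the limit of quantification (BLQ) collected on Day 1 pre-dose will be summarized as zero". On Day 1 the pegloticase sample is drawn only after the infusion, so in practice this rule concerns the polyglutamates.
- Later visits, for polyglutamates: "all post-baseline concentrations BLQ will be excluded from analysis".
- Reporting: "The number of BLQ values will be presented for pegloticase and MTX summaries".

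Protocol 9.3.3.1.1 adds that MTX or placebo stops when pegloticase stops, and that polyglutamate samples are then no longer taken.

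Protocol 9.6.6 names the PK population for these concentrations, as appropriate, and refers to a separate PK analysis plan. SAP 2.1 keeps the polyglutamate summaries within the SAP. The PK population also contains both arms.

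**The concern.** The evident use of a polyglutamate display by responder status is to relate MTX exposure to urate response. By Day 1 the MTX arm has been scheduled for six weekly MTX doses (two open-label, four blinded). The placebo arm has been scheduled for two, the last about four weeks or more earlier. Placebo-arm levels should therefore be lower, by an amount the documents do not state.

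If MTX works, placebo subjects make up a larger share of non-responders than of responders. The pooled responder mean then exceeds the pooled non-responder mean on Day 1, even if level and response are unrelated within the MTX arm. A reader of the table or plot could take that gap for an exposure-response relation.

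The later visits raise a second difficulty. The subjects behind each plotted mean are not the same at Day 1 and Week 14, so a change between those visits need not be a change in exposure.

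**Working it through.** **Inputs.** SAP 3.6 gives 145 randomized subjects and response rates of 71% (MTX) and 43% (placebo). At 2:1, 145 × 2/3 = 96.7, so I use 97 and 48. Half the planned 28-point effect is 57% versus 43%. Let r be the mean placebo-arm level divided by the mean MTX-arm level on Day 1. The documents give no polyglutamate levels or half-life, so r is assumed and run from 0% to 100%. The 33% value is only the share of scheduled MTX doses, 2 of 6, and not a kinetic estimate.

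**The plan's own figure.** For 90 versus 45 at 71%/43% and two-sided 0.05, the pooled rate is (63.9 + 19.35)/135 = 0.617. The null standard error is 0.0888 and the alternative standard error is 0.0879. Power = Φ[(0.28 − 1.96 × 0.0888)/0.0879] = 88.6%, which agrees with the stated 88%.

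**Arm mix at the planned rates.**
- Responders: 97 × 0.71 = 68.9 MTX and 48 × 0.43 = 20.6 placebo. Placebo share f_R = 20.6/89.5 = 0.231.
- Non-responders: 97 × 0.29 = 28.1 MTX and 48 × 0.57 = 27.4 placebo. Placebo share f_N = 27.4/55.5 = 0.493.

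At 57%/43% the same steps give f_R = 0.272 and f_N = 0.396.

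**Ratio of Day 1 means.** Set the MTX-arm mean to 1 and assume no relation between level and response within either arm:

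ratio = [(1 − f_R) + r f_R] / [(1 − f_N) + r f_N]

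At r = 0 and planned rates this is 0.769/0.507 = 1.52.

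| r (assumed) | 71% vs 43% | 57% vs 43% |
|---|---|---|
| 0% | 1.52 | 1.21 |
| 33% | 1.26 | 1.11 |
| 50% | 1.17 | 1.08 |
| 75% | 1.07 | 1.03 |
| 100% | 1.00 | 1.00 |

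Using 90/45 changes these by less than 0.01. With equal response rates the ratio is 1.00 at any r, and within either arm alone it is 1.00 by construction.

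**Sensitivity.** If 5% of each arm left before Day 1 (assumed: non-responders with no sample), the r = 0 planned-rate ratio would be 1.59. Dose reduction or discontinuation in the MTX arm during run-in, which SAP 3.5 allows, would raise r and lower the ratio.

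**The pooled overall mean.** On Day 1 it equals 97/145 + (48/145) r of the MTX-arm mean: 0.67, 0.78 and 0.83 at r = 0%, 33% and 50%.

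**After Day 1.** Two rules change who is in the means. BLQ values go from counted as zero to excluded, which should remove many placebo-arm values. Sampling also ends when infusions stop, and subjects who meet the uric acid stopping rule before or during Month 6 are non-responders under SAP 9.2.2, so non-responders from both arms leave the sampled set. The documents do not allow these two effects to be sized.

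**The case against.** The best counter-argument is that arm is what sets MTX exposure here. If MTX raises response and placebo subjects have lower polyglutamates, a higher pooled mean in responders is a true description. The within-arm comparison is not randomized either, since adherence, dose reduction and tolerability can affect both level and response. This stands as a reason not to forbid a pooled display. It does not rescue the pooled display as the only one: grouping by outcome is not protected by randomization, and the display cannot separate an arm effect from an exposure-response relation.

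Second, the table and figure shells are redacted, a separate PK plan is mentioned, and SAP 13.2.4 calls for group sizes by treatment in column headings. A split in the outputs therefore cannot be ruled out, and a reader should not infer that the outputs will lack one. None of these shows a split, though. The heading rule concerns format, and the column rule in SAP 6.1 addresses efficacy and safety summaries.

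Third, some protection exists already. SAP 10.2 requires a listing with treatment beside each concentration, BLQ counts, and medians and quartiles, so a block of zeros would be partly visible. The ratios above apply to means. The plot, however, shows means.

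Fourth, a reader might infer a distortion of at least 1.2 at the planned effect. That would hold only if placebo residuals were known not to exceed about half of MTX-arm levels, and nothing in the documents sets that ceiling.

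**Conclusion.** The point holds as a minor one. As written, SAP 10.2 pools the arms in a responder comparison of MTX exposure. Arm mix alone can give a Day 1 ratio of means between 1.0 and about 1.5 at the planned effect, and between 1.0 and about 1.2 at half of it. This rests on the planned response rates, on no relation within arm, and on assumed residual levels. The ratio is 1.00 if MTX has no effect on response or if placebo-arm levels equal MTX-arm levels.

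Two stronger readings are not supported. One is that the same distortion runs through all four visits, or that the Day 1 gap will disappear by Week 14 by a calculable amount. After Day 1, BLQ exclusion and the end of sampling both change the set, and MTX-arm levels may themselves change, so the documents support only the caution that a shift from Day 1 to Week 14 can reflect who is included. The other is that the trial's efficacy conclusion is at risk. The output is descriptive, and no primary or secondary test uses it.

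**What to change.** In SAP 10.2:
- present the polyglutamate summaries by treatment group;
- show the responder comparison and the PG3 and PG3-5 plot within the MTX arm, keeping a pooled version, if wanted, as an addition labelled as mixing arms;
- give n and the already planned BLQ counts by arm and responder status at each visit.

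If the separate PK plan already does this, a cross-reference in 10.2 is enough.

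The cost is a few sentences and some extra table columns, with no new data. The drawback is smaller groups: on Day 1 at the planned rates, about 69 responders and 28 non-responders in the MTX arm, against about 90 and 55 pooled.

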## **11. Safety**

Safety analyses will be based on the safety population and the MTX population, depending on the treatment period. The MTX population will be used for analysis of safety data during the MTX Tolerability period prior to randomization and the safety population will be used for analysis thereafter. For summaries by study period, the number of subjects included in the Safety Population for each period will be the number of subjects with data in that period (e.g. for the Pegloticase + IMM Period, subjects must have received pegloticase).

Safety will be assessed via AEs including AEs of special interest (AESI [i.e., IRs, anaphylaxis, gout flares, and cardiovascular events]), concomitant medication use (refer to Section 8.3), physical examinations, vital signs, clinical safety laboratory evaluations (complete blood count, chemistry, urine albumin:creatinine ratio), pregnancy testing (if applicable), and electrocardiograms (ECGs).

All safety information will be provided in subject listings.

### **11.1. Extent of Exposure**

Study drug exposure will be summarized from the MTX and placebo dosing calendar using the duration of treatment (in days), number of infusions, total dosage (mg) received for MTX or placebo and pegloticase, average dose (mg) received for MTX during MTX Tolerability, Run-in, and Pegloticase + IMM Period, average dose (mg) for placebo during Run-in and Pegloticase + IMM Period, and total dosage (mg) per dose overall. The MTX (or placebo) is supposed to be taken once weekly. The sequential dose number of MTX or placebo is defined by weekly. Any split doses taken within 48 hours are considered as one single dose, and the sum of the split doses is considered as the dosage for that dose number. The usage of folic acid, IR prophylaxis of fexofenadine in the evening prior to pegloticase infusion, IR prophylaxis of fexofenadine in the morning prior to the pegloticase infusion, acetaminophen, and methylprednisolone on the morning prior to pegloticase infusion will be summarized by number of subjects and percentage with compliance < 80% and ≥ 80%, in addition to being provided in listings. Interruptions in pegloticase infusions will be summarized. Reasons for infusion interruptions will be provided in the listings.

For the MTX Tolerability Assessment Period, the following will be summarized for the MTX population:

- Duration of treatment defined as (the last dose of MTX prior to the Week -4 visit date – first dose date of MTX in the MTX Tolerability Assessment Period) + 1 (summarized with descriptive statistics of mean, SD, median, minimum, and maximum)
- Total MTX dosage taken between the first and last dose dates in the MTX Tolerability Assessment Period, inclusive (in mg) (summarized with descriptive statistics of mean, SD, median, minimum, and maximum)
- Average MTX dose (mg) (total dosage for MTX Tolerability Period divided by number of doses taken during MTX Tolerability Period) (summarized with descriptive statistics of mean, SD, median, minimum, and maximum)

For the Run-in Period, the following will be summarized by treatment group for the Safety population:

- Duration of treatment defined as [the last dose of MTX or placebo prior to the Day 1 visit date – first dose date of MTX or placebo in the Run-in Period (Week -4)] + 1 (summarized with descriptive statistics of mean, SD, median, minimum, and maximum)
- Total MTX or placebo dosage taken between the first and last dose dates in the Run-in Period, inclusive (in mg) (summarized with descriptive statistics of mean, SD, median, minimum, and maximum)
- Average MTX or placebo dose (mg) (total dosage for Run-in Period divided by number of doses taken during Run-in Period) (summarized with descriptive statistics of mean, SD, median, minimum, and maximum)
- Number of subjects with dosage reductions (reduction in planned dose for reason of AE, abnormal labs, or titration down) from planned 15 mg/week.

For the Pegloticase + IMM Period, the following will be summarized by treatment group for the Safety Population:

- Pegloticase
  - Number of pegloticase infusions received overall per subject (summarized with frequency summary along with descriptive statistics of mean, SD, median, minimum, and maximum)
  - Duration in days between first and last pegloticase infusion, defined as (last infusion date – first infusion date) + 1 (summarized with descriptive statistics of mean, SD, median, minimum and maximum)
  - Number of incomplete infusions received (summarized with frequency summary along with descriptive statistics of mean, SD, median, minimum and maximum)
  - Number of interrupted infusions summarized with frequency summary along with descriptive statistics of mean, SD, median, minimum and maximum)
- At each scheduled Pegloticase infusion visit
  - Number of subjects not receiving MTX or placebo between previous infusion and current infusion (for subjects infused at current visit)
  - Number of subjects receiving a complete infusion (i.e. full dose administered)
  - Number of infusions administered without interruption
  - Number of subjects with an interrupted infusion
- MTX or placebo

This document is confidential.

- Duration of MTX or placebo dosing during the Pegloticase + IMM Period, defined as [the last MTX or placebo date – first MTX or placebo dosing date (on or after the date of the Day 1 visit)] + 1
- Cumulative MTX or placebo dosage (in mg) received during the Pegloticase + IMM period
- Average MTX or placebo dose (mg) (total dosage for Pegloticase + IMM Period divided by number of doses taken during Pegloticase + IMM Period) (summarized with descriptive statistics of mean, SD, median, minimum, and maximum)
- Number of subjects with dosage reductions (reduction in planned dose for reason of AE, abnormal labs, or titration down) from planned 15 mg/week.

For the overall study, the following will be summarized by treatment group:

- MTX
  - Duration of MTX dosing, defined as [the last MTX date – first MTX dosing date (on or after the date of the Day 1 visit)] + 1
  - Cumulative MTX dosage (in mg) received
  - Average MTX or placebo dose (mg) (total dosage overall divided by number of doses taken overall) (summarized with descriptive statistics of mean, SD, median, minimum, and maximum)
  - Number of subjects with MTX dosage reductions (reduction in planned dose for reason of AE, abnormal labs, or titration down) from planned 15 mg/week.
  - Total MTX or placebo dosage (mg) per dose overall

## **11.2. Treatment Compliance**

Other than the summarizations of Pegloticase infusions described in Section 11.1, the compliance with Pegloticase will not be summarized.

Compliance with MTX or placebo 15 mg will be summarized based on drug accountability data for the Safety Population for the duration of the study after randomization. Compliance will be calculated as  $100 \times (\text{the number of capsules taken divided by the expected number of capsules})$ . Subjects are expected to take 6 capsules (15 mg) each week. The number of capsules taken is defined as the number of capsules dispensed – number of capsules returned from the blinded bottles (i.e. excluding open label MTX given during MTX Tolerability Period). If a bottle is not returned, it will be assumed that the subject took all pills in the bottle and the number of capsules returned is set to 0. The expected number of capsules is defined as:

- $6 \times [\# \text{ of weeks between Week -4 visit date and the last infusion date}]$ . For subjects who complete pegloticase infusions through the end of the study, 6 will be added to the expected number of capsules (since subjects expected to take additional MTX/PBO dose after last infusion).

This document is confidential.

The # of weeks will be calculated as  $[(\text{end date} - \text{start date} + 7) / 7]$ , dates for prescribed dose are based on the MTX/PBO diary data.

Additionally, compliance with MTX or placebo during the Pegloticase + IMM period will be calculated from the MTX/PBO calendar log (a dosing diary where subjects recorded date, time and # of capsules taken each week). Compliance based on diary data is defined as  $100 \times (\text{number of MTX or placebo doses taken divided by the number of expected doses})$ . The number of MTX or placebo doses taken will be calculated by taking the number of MTX or placebo doses taken starting with the two most recent doses prior to the first pegloticase infusion up through the last pegloticase infusion. The expected number of doses is 2 times the number of pegloticase infusions received (as subjects should take 2 MTX or placebo doses in between each infusion).

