#### **9.4.2.2 Methotrexate and Placebo for Methotrexate**

MTX 2.5 mg tablets for oral administration during the MTX Tolerability Assessment Period (Week -6 through Week -4) will be provided to subjects as a commercially available generic.

MTX 2.5 mg tablets for oral administration during the Run-In Period (Week -4 through Day 1) and the Pegloticase + IMM Period (Day 1 through Week 52) will be provided to subjects as a methotrexate 2.5 mg tablet over-encapsulated in a size zero Swedish Orange capsule.

Placebo for methotrexate 2.5 mg for oral administration during the Run-In Period (Week -4 through Day 1) and the Pegloticase + IMM Period (Day 1 through Week 52) will be provided as a size zero Swedish Orange capsule with Avicel® filling.

A dosing calendar will be provided to subjects at the Week -6 Visit to record each dose of MTX or placebo for MTX and the date and time of each dose on each calendar day of MTX or placebo for MTX administration.

See [MTX Full Prescribing Information](#) for additional detail.

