#### **9.4.11 Treatment Compliance**

A dosing calendar will be provided to subjects at the Week -6 Visit for recording the dose/s of MTX/placebo for MTX and the date and time of each dose on each calendar day of MTX/placebo for MTX administration. The dosing calendar and bottle of MTX/placebo for MTX should be brought to each study visit for assessment of compliance. Adherence to the MTX/placebo for MTX regimen will also be recorded by the study coordinator at study visits in the eCRF by recording the date of each MTX/placebo for MTX dose (mg), frequency and time of each dose per calendar day. Subjects who have taken at least 80% of the protocol-specified amount of MTX/placebo for MTX will be considered compliant. Noncompliant subjects will be re-educated on compliance.

At study visits, the subject will be asked a Yes/No question whether folic acid, gout flare, and IR prophylaxis were administered.

Pegloticase will be administered at the study site by trained personnel. The date and time of infusion start and stop (inclusive of the 10-mL flush) will be recorded.

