### **5.4. Per-protocol Population**

The Per-protocol (PP) population will include all randomized subjects who receive at least 1 dose of pegloticase, are taking the 15 mg dose of MTX or placebo at the time of first pegloticase dose, and have no major protocol deviations that will challenge the validity of their data. The PP population will be used for analysis of the primary efficacy endpoint.

Major protocol deviations will be classified as exclusionary vs. non-exclusionary from the per-protocol population. Classification of exclusionary protocol deviations will occur prior to the unblinding of treatment groups after all subjects complete the Pegloticase + IMM period. Only exclusionary deviations that occurred prior to and including Week 24 will be used for classification. Exclusionary deviations include:

- Enrollment of a subject who did not satisfy the following inclusion/exclusion criteria (see Section 9.3 of the protocol):
  - Inclusion criteria #4 and #8
  - Exclusion criteria #13, #15, and #16
- Subject received treatment other than that to which he or she was randomized
- Compliance with MTX or placebo < 80% while receiving pegloticase
- Missing >20% of pegloticase infusions unless due to adverse event

This document is confidential.

- Any other deviation that has the potential to negatively impact the validity of the primary or secondary endpoints.

Compliance will be assessed based on the drug accountability data (per method defined in Section 11.1).

“Missed infusion” is defined as a subject not receiving an infusion at a scheduled visit through Week 22 (or not attending a scheduled infusion visit) prior to discontinuation of pegloticase treatment unless the reason for not receiving infusion is due to an adverse event. Subjects are allowed to discontinue pegloticase treatment for any reason and will not be excluded from the Per-Protocol population unless they miss >20% of infusions prior to the End of Pegloticase Visit for reasons other than adverse event.

Subjects with exclusionary deviations specified above that are due to COVID-19 (other than those due to suspected or confirmed infection) will be excluded from the PP Population.

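### Counting every capsule in an unreturned bottle as taken biases the per-protocol compliance test upward; separately, the diary formula overstates reported compliance when infusions are skipped

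*SAP*

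**What the plan says.** SAP 11.2 defines two compliance measures for blinded MTX or placebo.

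- **Accountability.** For the numerator, "The number of capsules taken is defined as the number of capsules dispensed – number of capsules returned from the blinded bottles". For a missing bottle, "If a bottle is not returned, it will be assumed that the subject took all pills in the bottle", and returned capsules are set to 0. For the denominator, "Subjects are expected to take 6 capsules (15 mg) each week", multiplied by the number "of weeks between Week -4 visit date and the last infusion date", plus 6 for subjects who complete the infusions. No cap at 100% is stated.
- **Diary.** The numerator counts doses from the two most recent before the first infusion up to the last infusion. For the denominator, "The expected number of doses is 2 times the number of pegloticase infusions received".

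SAP 5.4 makes compliance below 80% while on pegloticase a per-protocol exclusion, using deviations up to and including Week 24. It states that "Compliance will be assessed based on the drug accountability data" and refers to Section 11.1 for the method. SAP 5.4 also excludes subjects who miss more than 20% of infusions, unless an adverse event was the reason.

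Protocol 9.4.11 provides a dosing calendar and adds that "Adherence to the MTX/placebo for MTX regimen will also be recorded by the study coordinator at study visits", with date, amount and time of each dose.

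**The concern.** Treating a missing bottle as fully taken can raise a compliance score but never lower it. The score then decides who is removed from the per-protocol set for poor compliance. MTX is the only randomised difference in this trial, and the per-protocol analysis is meant to show the effect in subjects who took what they were assigned. A rule that can pass subjects who did not take it weakens that purpose and overstates reported compliance.

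Subjects who stop infusions early may be the most exposed. Their denominator ends at the last infusion, while the whole of an unreturned bottle is credited. Protocol 9.3.3.1.1 stops MTX or placebo together with pegloticase and drops compliance reconciliation afterwards, so the End of Pegloticase Infusions Visit is the remaining listed check. SAP 5.4 leaves early stoppers eligible for the per-protocol set.

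The diary measure has a different fault. Dosing is weekly whether or not an infusion is given, but its denominator shrinks by two with each skipped infusion.

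**Working it through.** **Reproducing the plan's own figures.** Each blinded active capsule holds a "methotrexate 2.5 mg tablet over-encapsulated in a size zero Swedish Orange capsule" (Protocol 9.4.2.2), so 15 / 2.5 = 6 capsules a week, as SAP 11.2 states. Weeks are (end date − start date + 7) / 7.

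- Week -4 to Week 50: (378 + 7) / 7 = 55 weeks; 55 × 6 = 330; plus 6 for completers = 336. This equals 56 weekly doses × 6.
- Week -4 to Week 24: (196 + 7) / 7 = 29 weeks, or 174 capsules. Without the added week it is 28 × 6 = 168. Cutting at Week 24 is an inference from SAP 5.4; the SAP 11.2 formula runs to the last infusion.

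**Accountability: effect of an unreturned bottle.**

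1. Nothing returned: score = dispensed / expected. At an assumed supply of 1.0, 1.1 or 1.25 times the expected amount, the score is 100%, 110% or 125%, whatever was taken.
2. Each untaken weekly dose in a lost bottle: 6/174 = 3.4 points and 6/168 = 3.6 points to Week 24; 6/336 = 1.8 points over the full course.
3. Unused capsules that lift true intake of 65% to 80%: 0.15 × 168 = 25.2 and 0.15 × 174 = 26.1 to Week 24; 0.15 × 336 = 50.4 over the full course.
4. One lost, wholly untaken bottle of B capsules: the lowest true intake that still passes is (0.80 × E − B) / E. Bottle size is not in the documents, so B is assumed:

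| B (assumed) | E = 174 (Week 24) | E = 336 (full course) |
|---|---|---|
| 30 | 62.8% | 71.1% |
| 60 | 45.5% | 62.1% |
| 100 | 22.5% | 50.2% |

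5. Early stopper, last infusion at Week 6: (70 + 7) / 7 = 11 weeks, 66 capsules. An assumed 30 unused, unreturned capsules add 30/66 = 45 points.

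**Diary: effect of skipped infusions.** Day 1 to Week 24 has 13 scheduled infusions, so 26 doses are expected. With 2 skipped, the formula expects 2 × 11 = 22.

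- 20 weekly doses taken: 20/22 = 91%, against 20/26 = 77% by calendar.
- All 26 taken: 26/22 = 118%, against 100% by calendar.

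**Does the diary fault reach the per-protocol set?** SAP 5.4 names accountability data, and that denominator is calendar weeks, so it does not shrink for skips before the last infusion. Take the 12 infusions to Week 22 (27 weeks), with infusions and their two MTX doses both omitted and all bottles returned. Accountability gives 25/27 = 92.6%, 23/27 = 85.2% and 21/27 = 77.8% for 1, 2 and 3 skips. Three skips are also 3/12 = 25% missed, which the separate infusion rule excludes unless an adverse event was the reason.

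**The case against.** A reader might infer that the diary formula keeps infusion-skippers in the per-protocol set. The documents do not support that: the diary is an additional measure that SAP 5.4 never names, and missed infusions have their own exclusion.

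Other points against the concern have weight:

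- **Catch-all exclusion.** SAP 5.4 also allows exclusion for any other deviation that could harm endpoint validity, classified before unblinding. A visible non-taker could be removed that way. This stands as a safeguard, but it is discretionary, and the missing-bottle rule hides the signal that would prompt it.
- **Records may be missing too.** The calendar and the bottle are brought to the same visits (Protocol 9.4.5 and 9.4.11), so a subject who keeps one may keep the other. This stands. The records are planned, not guaranteed, and that bottles go missing more often in non-takers is plausible rather than shown.
- **Interim counts.** Sites count capsules at each visit and re-dispense the bottle (Protocol 9.4.5). SAP 11.2 does not say whether those counts are used when the bottle is later lost.
- **The diary rule is deliberate.** SAP 11.2 explains it as two doses between infusions. As MTX cover per infusion received it has some sense, but a compliance percentage that reaches 118% does not measure that cleanly. The two pre-infusion doses also carry no date limit.
- **Low stakes.** The primary analysis is intention-to-treat and the per-protocol analysis is a supplemental repeat (SAP 9.2.3 and 9.2.4). Admitting non-takers would tend to dilute the contrast, which is conservative for superiority. This stands and sets the severity.

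**Conclusion.** The point holds, at minor severity. The unreturned-bottle rule biases the per-protocol compliance figure upward. A pass is certain for a subject who returns nothing, given supply at least equal to the expected amount. Otherwise it depends on how much is unreturned and on bottle size, which is not given. The gain per untaken weekly dose is 3.4 to 3.6 points if compliance is cut at Week 24, and 1.8 points over the full course. The number of subjects affected cannot be judged from the documents.

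The diary measure overstates compliance whenever infusions are skipped and MTX continues at all in the gap beyond what the reduced denominator expects, or when doses are omitted along with the infusion. This reaches the descriptive summary only. Neither fault touches the primary or the sequentially tested secondary analyses, and it would be wrong to read either as a threat to them.

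The cross-reference in SAP 5.4 is also wrong: Section 11.1 summarises exposure from the dosing calendar, while the accountability formula is in 11.2.

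**What to change.** 1. For an unreturned bottle, take the capsules used from the dosing calendar or eCRF dose log for that interval. If the log is blank, set the count to missing and decide per-protocol status at the classification of deviations already scheduled before unblinding. A half-taker who returned nothing would then score 50% from a complete log, not 100% or more.
2. Set the diary denominator to calendar weeks from 14 days before the first infusion to the last infusion, and count only doses dated in that span. With no skips this leaves the present figure unchanged (26 doses to Week 24); with 2 of 13 skipped, the two examples become 77% and 100%.
3. Change the SAP 5.4 cross-reference from Section 11.1 to 11.2.

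The cost is SAP wording and programming, with no new data collection. A few subjects may leave the supplemental per-protocol set.
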